10.5.2. Baseline Definition & Derivations

10.5.2.1. Baseline Definitions

In general, the subject level baseline (or study baseline) is defined as the value taken at visit 2 (randomization), and the period level baseline is defined as the pre-treatment value taken at the start of each treatment period (visit 2 and visit 5). Using these definitions the period baseline for treatment period 1 is the same as the subject level baseline.

For FEV₁ and Vital Signs, the baseline value at visit 2 will be taken from the “Pre Challenge” planned time.

The primary analysis will include as a covariate, the period baseline value as well as including as a covariate, the mean of the two period baseline values.

For the physical activity measures assessed by the biosensor, the period baseline will be derived using all the available data from the last 7 calendar days prior to, but not including the first clinic visit of the treatment period (Visit 2/5). For example, if the randomisation visit (Visit 2) was on the 18th May then the period baseline for treatment period 1 would be derived as the average of the non-missing data that is available from the 11th May to the 17th May inclusive.

10.5.2.2. Derivations and Handling of Missing Baseline Data

Change from baseline will be defined as the difference between the value of the endpoint at the time point of interest and the baseline value as defined in Section 10.5.2.1.

If the baseline for an endpoint is missing it will not be imputed using a different time point or derivation but will remain missing.

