8.3.3.4. Visit 4 and Visit 7 (Blinded Treatment Exercise Challenges)

Visit 4 and Visit 7 begin between 5 PM and 11 PM and are conducted over approximately 24 hours. Subjects will be required to attend three clinic visits during each 24-hour period for Visit 4 and Visit 7. The evening visit should begin at approximately the same time as Visit 1 (± 1 hour).

Dosing: At the beginning of Visit 4 and Visit 7, subjects will administer their evening doses of double-blinded study medication in the clinic and the time of dosing will be recorded. In addition to administering the evening dose, vital signs will be measured and a review of concomitant medication and AEs performed.

Subjects will return to the clinic 12 (± 1) hours and 23 (± 1) hours after evening dosing for exercise challenge testing.

Pre-exercise FEV₁: At least two valid spirometry efforts with full FEV₁ and FVC maneuvers should be obtained just prior to each exercise challenge.

From this spirometry testing, the target FEV₁ values #2 and #3 (Section 8.3.1.1) should be determined based on the pre-exercise FEV₁.

Exercise challenge testing: Exercise challenge testing will occur at 12 (± 1) hours and 23 (± 1) hours after administering the evening dose. (The 12-hour exercise challenge and spirometry measurements should occur prior to dosing of the study medication).

Post-exercise Serial Spirometry: Following the eligibility exercise challenge at each visit, serial spirometry (FEV₁) will be performed at 5, 10, 15, 30, 45 and 60 minutes post-exercise.

Washout Medication Dosing: At the end of Visit 4, the washout medication should be dispensed and first evening dose administered following completion of the 23-hour post evening dose exercise challenge/serial spirometry, and prior to the subject's leaving the clinic.

8.3.3.5. Visit 5

Treatment period 2 baseline FEV₁: Spirometry will be performed at Visit 5 at approximately the same time as at Visit 1 (± 1 hour). The FEV₁ should be measured approximately 12 hours (± 1 hour) after dosing with the washout medication. At least two valid spirometry efforts should be obtained.

Dosing: Subjects will administer their evening doses of double-blinded study medication following the spirometry.

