10.4. Key Elements of Analysis Plan

Where possible, data from subjects who withdraw prematurely from the study will be included in any analyses. Specific details for inclusion will be detailed in the RAP but, in general, if a subject has completed a treatment period, including both exercise challenges and FEV₁ evaluations, then the data for that period will be included in the analysis.

Specifically if a subject has completed the first exercise challenge at 12 hours post-dose, as well as the FEV₁ evaluations after this challenge, but has not completed the second exercise challenge at 23 hours post-dose, then the data for the 12 hour post-dose time point will be included, but will not be carried forward to replace the missing 23 hour time point.

Any tests for interactions will be 2-sided at the 10% level of significance. In all cases, if any assumptions of the proposed methods of analyses are not met, alternative methods of analyses will be used.

The baseline FEV₁ for all endpoints will be the pre-treatment FEV₁ value obtained at the start of each Treatment Period (Visit 2 or Visit 5).

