10.4.1.1. Primary Analysis

The primary efficacy end point is maximal percent decrease from pre-exercise FEV₁ following exercise challenge at 12 hours post-dose following two weeks of treatment. Maximal percent decrease will be defined as the percent change from pre-exercise FEV₁ to the minimum FEV₁ collected within one hour following exercise challenge at 12 hours post-dose. Pre-exercise FEV₁ will be defined as the FEV₁ value collected prior to the exercise challenge test at 12 hours post-dose.

The primary analysis is a comparison of the estimated means of the two treatment groups in maximal percent decrease in FEV₁ from pre-exercise at 12 hrs post-dose using a LMM to adjust for covariate effects. The LMM will include the following covariates: treatment, subject-level mean of the pre-treatment FEV₁ period baselines (mean of the 2 period baselines per subject), centered period-level baseline FEV₁ (period baselines centered using subject-level mean of the pre-treatment FEV₁ period baselines), gender, age, treatment period and smoking history as fixed effects, and a random intercept for each subject.

Details will be provided in the RAP of alternative analyses methods to be used in the event that distributional assumptions do not hold (e.g. if the distribution appears to be heavily skewed).

Mean post-exercise minimum FEV₁ measurements and mean maximal percent decrease from pre-exercise FEV₁ will be summarized with descriptive statistics by treatment group. Summaries and analyses for the primary endpoint will be provided for both the ITT and PP populations.

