7.1.2. Planned Primary Efficacy Statistical Analyses

Primary Statistical Analyses
Endpoint(s)

 Maximal percent decrease from pre-exercise FEV₁ following exercise challenge at 12 hours post evening dose at the end of the 2-week treatment period
Populations

 This analysis will be performed on both the Intent-to-Treat (ITT) and the Per Protocol (PP) populations.
Model Specification

The mixed model repeated measures (MMRM) model will include the following covariates (with example variable names): treatment (ptrtcd), sex (sex), age (age), treatment period (pernum), smoking history (supkyr: number of pack years), period baseline FEV₁ (pbli) and the mean of the two period baseline FEV₁ values (mpbli) as fixed effects, and a random intercept for each subject (subjid). A SAS procedure of the following structure will be used:
 <pre>proc mixed data=start cl nobound ; class subjid ptrtcd sex pernum ; model maxd = ptrtcd pernum pbli mpbli age sex supkyr / solution ddfm=kr ; random int / subject=subjid type=simple ; repeated pernum / subject=subjid type=simple ; lsmeans ptrtcd / diff cl e om=OMdset at (age mpbli)=(&agem. &mpblim.) ; ods output lsmeans=lsmeans ; ods output diffs=diffs ; run ;</pre>
Where OMDset is a dataset with a row for every period-subject combination that contains all of the covariates and mpblim and agem are macro variables containing the means for mpbli and age for the subjects used in the analysis. These are used to derive the adjusted means using coefficients which are based on the subjects used in the analysis.
Model Checking & Diagnostics

 Refer to Appendix 11: Model Checking and Diagnostics for Statistical Analyses.
Model Results Presentation

 The adjusted means for each treatment and the estimated treatment difference for the treatment comparison will be presented together with a 95% confidence interval for the difference and a p-value. The adjusted treatment difference and 95% confidence interval will be plotted.

Sensitivity and Supportive Statistical Analyses
Maximal Decrease (L) from Pre-Exercise FEV₁ Analysis
This supporting analysis will be analysed using a model of the same structure as described for the primary analysis.

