10.7. Appendix 7: Premature Withdrawals & Handling of Missing Data

10.7.1. Premature Withdrawals

Element	Reporting Detail
General	
 Subject study completion is defined in the protocol as completing all phases of the study including the follow-up phone contact. Withdrawn subjects will not be replaced in the study. All available data from subjects who were withdrawn from the study is included in listings and where possible any available data from withdrawn subjects is included in any summaries or analyses

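### As written, the primary model drops a valid Period 1 outcome when the subject has no usable Visit 5 baseline, although the protocol says such data are included

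*SAP*

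**What the plan says.** **Model.** SAP 7.1.2 lists "the mean of the two period baseline FEV₁ values (mpbli) as fixed effects", and the code reads "model maxd = ptrtcd pernum pbli mpbli age sex supkyr / solution ddfm=kr". Protocol 10.4.1.1 specifies the same covariate, the "mean of the 2 period baselines per subject", with a centred period-level baseline.

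**Where the baselines come from.** SAP 10.5.2.1 takes them before treatment at Visit 2 and Visit 5. At Visit 5 the order is fixed in Protocol 8.3.3.5: "Subjects will administer their evening doses of double-blinded study medication following the spirometry".

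**Missing baselines.** SAP 10.5.2.2 says that if a baseline is missing "it will not be imputed using a different time point or derivation but will remain missing". SAP 10.1.1 treats FEV₁ values labelled Unacceptable as missing in both the ITT and the Per Protocol populations.

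**Withdrawn subjects.** Protocol 6.4.2 says data collected up to withdrawal will be used. Protocol 10.4 says that if a subject has completed a treatment period, "then the data for that period will be included in the analysis". It adds that a completed 12-hour challenge counts even when the 23-hour one was not done. SAP 10.7.1 says "where possible any available data from withdrawn subjects is included in any summaries or analyses". SAP 2.1 declares no change from the protocol's analysis, and the ITT definition in SAP 4 has no two-baseline condition.

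**The concern.** A subject who has the 12-hour challenge at Visit 4 and leaves then or during washout has an observed primary outcome and an observed Period 1 baseline, but no Visit 5 baseline. With no two-value mean, mpbli is missing and the row is deleted. A subject who stays in the study but whose Visit 5 FEV₁ is missing or Unacceptable loses the Period 1 row for the same reason.

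This reaches four of the six tests in the hierarchy (SAP 10.10.1): maximal percent fall at 12 and 23 hours, and the weighted mean at 12 and 23 hours. The two recovery tests (SAP 7.2.2.2) use the period baseline only and keep the Period 1 rows, so the analysis set changes from test to test within one hierarchy.

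At stake is mainly who is in the gatekeeper analysis. It would be conditional on having a usable Visit 5 FEV₁. Protocol 6.4.1 makes outcome-related loss before Visit 5 foreseeable: it withdraws subjects who need certain rescue treatment after a challenge, and those with a severe exacerbation or asthma worsening during washout. The documents do not say how often this is expected.

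**Working it through.** **1. The plan's own figure.** Inputs from Protocol 10.2.1: difference 5, within-subject SD 8, 56 evaluable subjects, two-sided 5%. Standard error = 8 × √(2/56) = 1.512. Noncentrality = 5/1.512 = 3.31. On 54 degrees of freedom the power is 90.1%, as in Table 5. Also 66 × 0.85 = 56.1. The plan's figure reproduces, and it counts only subjects evaluable in both periods.

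**2. Who is affected.** At most 66 − 56 = 10 subjects are expected to withdraw.

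| Situation | Both baselines? | Period 1 row, primary model as written |
|---|---|---|
| Withdraws before the Visit 4 12-hour challenge | No | No outcome to lose |
| Withdraws after that challenge, before Visit 5 spirometry | No | Deleted |
| Visit 5 FEV₁ missing or Unacceptable | No | Deleted |
| Withdraws after Visit 5 spirometry | Yes | Kept |

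In a constructed dataset with 56 completers, 5 washout withdrawals and 5 Period 2 withdrawals, the model as written used 61 subjects and 56 × 2 + 5 = 117 rows. With mpbli taken from the available baselines it used all 66 subjects and 122 rows.

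**3. Precision.** For *n* completers and *k* Period-1-only subjects split evenly between sequences, in a random-intercept model with treatment and period, SE = √[2 × 8² / (n + k(1 − ρ)/2)], where ρ is the intraclass correlation. The documents give neither *k* nor ρ, so *k* = 0–10 and ρ = 0.2–0.8 are assumptions. Power below uses the normal approximation, which gives 91.1% at *k* = 0.

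| k kept | SE, ρ = 0.2 | SE, ρ = 0.8 | Power | Equivalent completers |
|---|---|---|---|---|
| 0 | 1.512 | 1.512 | 91.1% | 56 |
| 5 | 1.486 | 1.505 | 91.3–92.0% | 56.5–58 |
| 10 | 1.461 | 1.499 | 91.6–92.8% | 57–60 |

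Example: *k* = 10, ρ = 0.2 gives √(128/60) = 1.461.

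**4. Bias.** This needs an assumption with no source in the documents: that withdrawal before Visit 5 becomes more likely with a larger Period 1 fall. Simulated with 66 subjects, true difference −5, within-subject SD 8 and between-subject SD 6–10:

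- All 15% lost before Visit 5, log-odds rising 0.10–0.15 per percentage point: the estimate with these subjects dropped is about −4.75 to −4.89. With them kept it is −5.0, within simulation error.
- Same loss, slope 0.05: about −4.95.
- About 3 of 66 lost in that window, slopes 0.10–0.15: about −4.89 to −4.94.

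The largest of these shifts is 0.25, or 0.25/1.51 = 0.17 of a standard error, and all are towards zero.

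**The case against.** The best defence is that the SAP does not actually order the exclusion. SAP 10.5.2.2 speaks of the baseline for an endpoint, directly after defining change from baseline, and does not name mpbli. A programmer could average whatever baselines exist and claim to comply. Protocol 10.4 and SAP 10.7.1 are also qualified (where possible, in general), Protocol 10.4 leaves details to the analysis plan, and the two-baseline mean is itself in the protocol.

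Much of this stands. A reader might infer that the SAP expressly forbids a one-value mean; it does not, and the exclusion follows only from reading the passages together. But a single value is a different derivation from a mean of two, so exclusion is the natural result of running the code as printed. Protocol 6.4.2 and the 12-hour sentence in Protocol 10.4 say plainly that such data are used. If the text is instead thought ambiguous, membership of the gatekeeper analysis is left to the programmer, which also needs settling.

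It is also fair to say that the timing of withdrawal is unknown, that 10 is a ceiling, and that the simulated selection is strong: slopes of 0.10–0.15 multiply the odds of withdrawal by 2.7–4.5 per 10-point fall.

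**Conclusion.** The point holds for subjects with a valid Period 1 12-hour endpoint and no usable Visit 5 FEV₁. For them, the primary model as written and the inclusion rules cannot both be followed, and the SAP declares no departure from the protocol.

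Two stronger readings are tempting and are not supported. The first is that everyone who completes Period 1 and then withdraws is lost. Visit 5 spirometry precedes the first Period 2 dose, so later withdrawals keep their Period 1 row. The second is that the trial loses planned power. The 90% rests on completers only, so the exclusion gives up a small bonus: at most 4 completers' worth, with 10 affected subjects and ρ = 0.2.

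The size is small on any of the assumptions tried. Bias arises only if leaving before Visit 5 depends on Period 1 response, and in the scenarios examined it works against showing a difference. The case for acting is that a gatekeeper ITT analysis should not lose protocol-included outcomes through an undefined covariate when defining it costs almost nothing.

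**What to change.** Before unblinding, state in SAP 7.1.2 and 10.5.2.2 that mpbli is the mean of the available period baselines, as an explicit exception to the no-derivation rule, so that every observed primary value with its own observed period baseline enters the ITT model. For a subject with one baseline, mpbli then equals that baseline and the protocol's centred term is zero, so no value is invented.

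Do not set a missing period baseline (pbli) equal to mpbli. For a subject with a Period 2 outcome but no Visit 5 FEV₁, that would carry the Visit 2 value into Period 2, which SAP 10.5.2.2 bars. It could also spread to other models and endpoints that use the period baseline. Such a subject contributes the Period 1 row only.

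Report the number of subjects with only one baseline. The same wording should cover the ACQ-5 change model (SAP 7.2.2.6), which uses a two-baseline mean of ACQ-5 scores. If the sponsor prefers to exclude these subjects, the SAP should say so, declare it as a departure from Protocol 10.4 and give the number affected.

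Cost: one SAP sentence and one derivation step, with no new data.

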10.5.3. Reporting Process & Standards

Reporting Process	
Software	

 The currently supported versions of SAS software will be used. 	
Reporting Area	
HARP Server	: uk1salx00175
HARP Area	: /arenv/arprod/gw685698_gw642444/mid201832/final/
QC Spreadsheet	: \\hlwdsntv006a\med_ds_rgm\Projects\Respiratory & Inflammation\Horizon\201832 (Exercise study)\Statistics\QC Tracking\
Analysis Datasets	

 Analysis and reporting (A&R) datasets will be created according to Integrated Data Standards Library (IDSL) standards. 	
Generation of RTF Files	

 RTF files will be generated. 	

Reporting Standards	
General	

 The current GSK Integrated Data Standards Library (IDSL) will be applied for reporting, unless otherwise stated: 
 4.03 to 4.23: General Principles 5.01 to 5.08: Principles Related to Data Listings 6.01 to 6.11: Principles Related to Summary Tables 7.01 to 7.13: Principles Related to Graphics 	
Formats	

 All data will be reported according to the treatment the subject was randomized to unless otherwise stated. Numeric data will be reported at the precision collected on the eCRF or recorded in the raw dataset if from non eCRF sources. For summaries and analyses the decimal places shown below will be applied in the data displays: 	

Reporting Standards		
Specification of Number of Decimal Places for Descriptive Statistics		
Label	Description	No. of decimal places (dp) more than raw data
N	Number of subjects in the treatment group	Always present to 0 dp
n	Number of subjects with non-missing values	Always present to 0 dp
Mean	Arithmetic Mean	1 dp
SD	Standard Deviation	2 dp
Median	Median	1 dp
Min.	Minimum	0 dp
Max.	Maximum	0 dp
Specification of Number of Decimal Places for Statistical Analysis		
Label	Description	No. of decimal places (dp) more than raw data
LS Mean	Adjusted mean for the treatment group	1 dp
LS Mean Change	Adjusted mean change from baseline for the treatment group	1 dp
Std Err	Standard error	2 dp
Difference	Treatment difference	1 dp
Odds Ratio	Treatment odds ratio	Always present to 2 dp
95% CI	95% Confidence interval around treatment difference/ratio	Same number of dp as the difference/ratio
p-value	p-value	Always present to 3 dp (or <0.001 or >0.999)
Planned and Actual Time		

 Reporting for tables, figures and formal statistical analyses : 
 Planned time will be used in figures, summaries, statistical analyses and calculation of any derived parameters, unless otherwise stated. Reporting for Data Listings: 
 Planned and actual time will be shown in listings (Refer to IDSL Statistical Principle 5.05.1). Unscheduled or unplanned measurements will be presented within the subject's listings. 		
Unscheduled Visits		

 Unscheduled visits will not be included in summary tables or figures. All unscheduled visits will be included in listings. 		
Descriptive Summary Statistics		
Continuous Data	Refer to IDSL Statistical Principle 6.06.1	
Categorical Data	N, n, frequency, %	

Reporting Standards
Graphical Displays

• Refer to IDSL Statistical Principals 7.01 to 7.13.• The programs for statistical analysis tables will create SAS datasets with the unrounded numbers from the statistical models to be used in any graphs. This will include all LS means, standard errors, treatment differences or ratios and confidence intervals. This will be done for all analysis tables regardless of whether or not a figure is planned as part of SAC.• The programs for all graphical displays will additionally create a CSV file with the final data that is used in the graph in order to allow the graph to be redrawn for any potential publication requirement in the future.

10.6. Appendix 6: Derived and Transformed Data

10.6.1. General

Multiple Measurements at One Time Point

 Subjects having both High and Low values for Normal Ranges at any post-baseline visits for safety parameters will be counted in both the High and Low categories of "Any visit post-baseline" row of related summary tables. This will also be applicable to relevant Potential Clinical Importance summary tables.
Time Since Study First Dose / Time Since Period First Dose

 Calculated as the number of days from the date of first dose: 
 Ref Date = Missing → Time Since First Dose = Missing Ref Date < First Dose Date → Time Since First Dose = Ref Date – First Dose Date Ref Data ≥ First Dose Date → Time Since First Dose = Ref Date – (First Dose Date) + 1
Study Day / Period Day

 Study day will be calculated as the number of days from the Visit 1 (Screening) visit: 
 Ref Date = Missing → Study Day = Missing Ref Date < Visit 1 Date → Study Day = Ref Date – Visit 1 Date Ref Data ≥ Visit 1 Date → Study Day = Ref Date – (Visit 1 Date) + 1 For a treatment period, the dates of the first and last clinic visits for that treatment period will be used as the period start date and the period end date. For the washout period, imputed dates will be used. The washout period start date will be the day after the period end date for the previous treatment period and the washout period end date will be the day before the period start date for the next treatment period. Period day will be calculated as the number of days from the period start date: 
 Ref Date = Missing → Period Day = Missing Ref Date < Period Start Date → Period Day = Ref Date – Period Start Date Ref Data ≥ Period Start Date → Period Day = Ref Date – (Period Start Date) + 1

10.6.2. Study Population

Demographics
Age

 GSK standard IDSL algorithms will be used for calculating age where birth date will be imputed as follows: 
 Any subject with a missing day will have this imputed as day '15'. Any subject with a missing date and month will have this imputed as '30th June'. Birth date will be presented in listings as 'YYYY'. Completely missing dates of birth will remain as missing, with no imputation applied. Consequently, the age of the subject will not be calculated and will remain missing. Age, in whole years, will be calculated with respect to the date of screening (Visit 1).

Demographics
Body Mass Index (BMI)

 Calculated as Weight (kg) / [Height (m)²]
Race

The high level FDA race categories and designated Asian subcategories are:
 
 1. African American/African Heritage 2. American Indian or Alaska Native 3. Asian 
 a. Central/South Asian Heritage b. Japanese/East Asian Heritage/South East Asian Heritage c. Mixed Asian Heritage (only required if data exists) 4. Native Hawaiian or other Pacific Islander 5. White 
These will be summarized along with all combinations of high level categories which exist in the data. All five of the high level race categories and the two Asian subcategories must appear on the display even if there are no subjects in a particular category, but combinations that do not exist in the data do not need to be represented. Combinations will be represented as the concatenation of the high level category terms, e.g., "White & Asian." The designated Asian subcategories will not be summarized as combinations with other categories.
 
In addition the twelve standard race categories collected on the IDSL eCRF page will be summarized along with categories for mixed race. The categories are:
 
 1. African American/African Heritage 2. American Indian or Alaska Native 3. Asian - Central/South Asian Heritage 4. Asian – East Asian Heritage 5. Asian – Japanese Heritage 6. Asian – South East Asian Heritage 7. Asian – Mixed Race 8. Native Hawaiian or other Pacific Islander 9. White – Arabic/North African Heritage 10. White – White/Caucasian/European Heritage 11. White – Mixed Race 12. Mixed Race 
"Asian – Mixed Race" is only used if more than one Asian category is selected, but no non-Asian races. Similarly, "White – Mixed Race" is only used if both of the White categories are selected, and

Demographics

no non-White races. If multiple races of different types are selected, then the overall “Mixed Race” category is used.

A subject will only be represented in a single category. A subject who selects a combination of races will be counted as “Asian – Mixed Race,” “White – Mixed Race,” or “Mixed Race,” but not in each of the constituent terms. Therefore the counts will add up to the total number of subjects with a response, and the percentages will add to 100%.

Extent of Exposure

Exposure will be calculated for each type of inhaler (DISKUS and ELLIPTA) separately. The number of days on study drug for each subject and treatment period will be calculated as (date treatment stopped – date treatment started) + 1. The treatment start and stop dates used will be the earliest and latest of all dates recorded for the subject and treatment period in question.

Treatment Compliance

Overall percentage treatment compliance for every subject will be calculated for each type of inhaler (DISKUS and ELLIPTA) and for each treatment period separately.

Compliance for the DISKUS and ELLIPTA will be based on the total number of inhalations taken from each type of inhaler and the expected number of inhalations to be taken. The expected number of inhalations will be derived as the expected number of inhalations per day (from each inhaler) multiplied by the number of days on study drug for the treatment period in question based on the subjects treatment start and stop date for that type of inhaler.

The total number of inhalations taken will be based on the dose counter for each type of inhaler. If there is no dose counter information at all for a given treatment period then the compliance will be missing, however, as long as the information from one dose counter is present, the compliance for that treatment period will be calculated. If a dose counter start count is missing then it will be assumed to be 30 for the ELLIPTA and 60 for the DISKUS.

In each calculation, all inhalers dispensed will be used, provided the dose counter stop counts are non-missing. The following formula will be used:

$$\text{Overall_Compliance} = \left(\frac{\text{Total_Number_of_Inhalations_Taken}}{\text{Expected_Inhalations} \times (\text{Stop_Date} - \text{Start_Date} + 1)} \right) \times 100$$

Where *Total_Number_of_Inhalations_Taken* is the total number of doses taken from all DISKUS or ELLIPTA inhalers in the treatment period in question, *Expected_Inhalations* is equal to 2 for the DISKUS and 1 for the ELLIPTA and *Start_Date* and *Stop_Date* are the earliest treatment start date and the latest treatment stop date recorded for all of the inhalers used in the calculation.

